4.6.2.2. Serious Adverse Events

An individual listing of all AEs including preexisting conditions will be provided. A separate listing will include AEs that led to permanent discontinuation from the study drug. In addition, a listing of AEs that occur more than 30 days after study treatment discontinuation will be provided.

With the International Conference on Harmonisation (ICH) E2A guideline, a SAE is any AE that results in 1 of the following outcomes:

- death
- initial or prolonged inpatient hospitalization
- a life-threatening experience (that is, immediate risk of dying)
- persistent or significant disability/incapacity
- congenital anomaly/birth defect
- considered significant by the investigator for any other reason

The number and percentage of patients who experienced any ICH-defined SAE will be summarized by treatment group during the treatment and follow-up periods using MedDRA PT nested within SOC. Events will be ordered by decreasing frequency within SOC in the LY3471851 1800µg treatment group. In addition, the SAEs will be summarized by treatment group using MedDRA PT without SOC. An individual listing of all SAEs will be provided.

4.6.3. Adverse Events of Special Interest

4.6.3.1. Infections

Infections will be defined using all PTs from the MedDRA Infections and Infestations SOC. Serious infection will be defined as all the infections that meet the SAE criteria.

The number and percentage of patients with TEAEs of infections, serious infections, and infections resulting in study drug discontinuation will be summarized by treatment group using MedDRA PTs.

The number and percentage of patients with TEAEs of infections by maximum severity will be summarized by treatment group using MedDRA PTs.

For infections of special interest (serious infections, potential opportunistic infections [POIs], herpes zoster, and herpes simplex), the IR (for detail, see Section 4.6) and 95% CI will be calculated.

Treatment-emergent infectious events will be reviewed in context of other clinical and laboratory parameters. A listing of patients experiencing treatment-emergent infectious AEs will be provided. The listing will include patient demographics, treatment group, treatment start and stop dates, infectious event, event start and stop dates, total leukocytes, total lymphocytes, absolute neutrophils, event seriousness, and event outcome.

The infectious TEAE will be further analyzed in terms of potential opportunistic infection, herpes zoster, and herpes simplex. A summary of hepatitis B virus (HBV) deoxyribonucleic acid (DNA) monitoring results and association between infection and neutropenia/lymphopenia will also be provided in the context of infections.

Potential Opportunistic Infections

Potential opportunistic infections will be identified according to 2 different approaches.

First, POIs will be identified from TEAEs based on a Lilly-defined list of MedDRA PTs shown in 6.8. These PTs are a subset of terms from the Infections and Infestations SOC.

Second, a list of all the infection details captured from the infection-specific eCRF (including primary/secondary infecting organism and infection site) will be provided. Of note, the infecting organism that was entered as free text by the investigator (instead of as a selection from the pull-down list) will also be provided.

The summary analysis of POIs identified using the 2 approaches above will be provided. Each case meeting the case definition for an opportunistic infection will be summarized by PT nested under infection pathogen. Events will be ordered by decreasing frequency of pathogen nested under pathogen species (mycobacteria, bacteria, fungal, viral, parasites). The order of frequency will be determined using the LY3471851 1800µg group.

Potential opportunistic infections identified through these approaches will be combined in 1 list for medical assessment for final classification of whether the case definition was met according to the consensus paper after database lock (i.e., Winthrop 2015). An additional summary may be conducted based on medical assessment.

Herpes Zoster

A summary table of herpes zoster will be provided. Herpes zoster will be defined based on the MedDRA PTs as listed under Herpes zoster (any form) (II) in 6.8, excluding Varicella virus text (10070444). The summary table will also include event maximum severity, seriousness, whether resulting in temporary study drug interruption, whether resulting in study drug discontinuation, whether treated with antiviral medication, and event outcome.

If a patient has more than 1 event of herpes zoster, the event with the maximum severity will be used in these summary tables. If more than 1 event of herpes zoster occurs with the same severity, the event with the longest duration will be used in the summary table.

Herpes Simplex

A summary analysis of herpes simplex will be provided. Herpes simplex will be defined based on the MedDRA PTs as listed under Herpes simplex (invasive disease only) (IV) in 6.8. The summary table will include event maximum severity, seriousness, whether resulting in temporary study drug interruption, whether resulting in study drug discontinuation, and whether treated with antiviral medication. Antiviral medication will be selected based on ATC code level 2 “antiviral for systemic use.”

If a patient has more than 1 event of herpes simplex, the event with the maximum severity will be used in these summary tables. If more than 1 event of herpes simplex occurs with the same severity, the event with the longest duration will be used in the summary table.

HBV DNA

A listing of patients with detectable HBV DNA will be provided.

HBV DNA status (not detectable, detectable but not quantifiable [ie, <29 IU/mL], quantifiable [ie, ≥29 IU/mL]) will be summarized by treatment group stratified by baseline HBV serology status, specifically:

- HBsAb- / HBcAb-
- HBsAb+ / HBcAb-

- HBsAb+ / HBcAb+
- HBsAb- / HBcAb+

Association between Infection and Neutropenia/Lymphopenia

To evaluate the association between infection and neutropenia and also between infection and lymphopenia, the frequency of infections will be provided by the worst Common Terminology Criteria for Adverse Events (CTCAE) grades of neutropenia and lymphopenia, respectively. Infection outcomes considered for this analysis are any treatment-emergent infection, serious infection, and herpes zoster. For this analysis, no statistical comparison will be provided.

In addition, a summary table will be provided for treatment-emergent infections that were preceded or accompanied by neutropenia/lymphopenia. For this analysis, neutropenia is defined as CTCAE Grade 2 or greater. Infection events with onset date ≤ 14 days before or after the Grade 2 neutrophil/lymphocyte count collection date will be considered as infections preceded or accompanied by neutropenia.

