10.6. Appendix 6: Examples of Infections That May Be Considered Opportunistic in the Setting of Biologic Therapy

The following table lists examples of infections that may be considered opportunistic in the setting of biologic therapy (adapted from Winthrop et al.¹⁶). This table is provided to aid the investigator in recognizing such infections. This list is not exhaustive. Infections will be categorized by Lilly as opportunistic according to *Opportunistic Infections and Biologic Therapies in Immune-Mediated Inflammatory Diseases: Consensus Recommendations for Infection Reporting during Clinical Trials and Postmarketing Surveillance* by Winthrop et al.¹⁶

Examples of Infections That May Be Considered Opportunistic in the Setting of Biologic Therapy

Bacterial
Bartonellosis (disseminated disease only)
Campylobacteriosis (invasive disease only)
Legionellosis
Listeriosis (invasive disease only)
Nocardiosis
Tuberculosis
Non-tuberculous mycobacterial disease
Salmonellosis (invasive disease only)
Shigellosis (invasive disease only)
Vibriosis (invasive disease due to Vibrio vulnificus)
Viral
BK virus disease including polyomavirus-associated nephropathy
Cytomegalovirus disease
Hepatitis B virus reactivation
Hepatitis C virus progression
Herpes simplex (invasive disease only)
Herpes zoster (any form)
Post-transplant lymphoproliferative disorder (Epstein-Barr virus)
Progressive multifocal leukoencephalopathy (PML), John Cunningham (JC) virus
Fungal
Aspergillosis (invasive disease only)
Blastomycosis
Candidiasis (invasive disease or oropharyngeal, esophageal. Not isolated lingual.)

Coccidioidomycosis
Cryptococcosis
Histoplasmosis
Paracoccidioides infections
Penicilliosis
Pneumocystosis
Sporotrichosis
Other invasive molds: Mucormycosis (zygomycosis) (Rhizopus , Mucor , and Lichtheimia), Scedosporium/Pseudallescheria boydii , Fusarium
Parasitic
Leishmaniasis (visceral only)
Strongyloidiasis (hyperinfection syndrome or disseminated disease)
Microsporidiosis
Toxoplasmosis
Trypanosoma cruzi infection (Chagas' disease progression) (disseminated disease only)
Cryptosporidiosis (chronic disease only)

Source: adapted from Winthrop et al.¹⁶

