4.6.3.3. Malignancies

Malignancies will be identified using terms from the malignant tumors SMQ (SMQ 20000194). Malignancies excluding nonmelanoma skin cancers (NMSC) and NMSC will be reported separately.

A listing including all malignancy cases will be provided. An NMSC flag will be provided using the following MedDRA PTs (the list will be updated depending on the MedDRA version used for analysis):

- Squamous cell carcinoma of skin (10041834)
- Bowen's disease (10006059)
- Basal cell carcinoma (10004146)
- Basosquamous carcinoma (10004178)
- Basosquamous carcinoma of skin (10004179)
- Squamous cell carcinoma (10041823)
- Skin squamous cell carcinoma metastatic (10077314)
- Skin cancer (10040808)
- Carcinoma in situ of skin (10007390)

The number and percentage of patients with TEAE-associated malignancies excluding NMSC and NMSC will be summarized by treatment group. In addition, the IR (for detail, see Section 4.6) and 95% CI will be calculated for the overall observation time. All cases identified by malignant tumors SMQ will be assessed after database lock by the medical team to determine (1) confirmed NMSC cases and (2) symptom and date that triggered the malignancy investigation or diagnosis. An additional listing based on medical review may also be provided if deemed necessary. All cases reported in the study database or by Lilly Safety System (LSS) report, disregarding the length of gap between the last treatment dose date and the event date will be included.

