Leishmaniasis (Visceral only) (IV)		Visceral leishmaniasis	10047505	Narrow
		Leishmaniasis	10024198	Broad
Strongyloides (hyperinfection syndrome and disseminated forms only) (IV)		None		Narrow
	Strongyloidiasis	10042254	Broad	

Category	Potential Opportunistic Infection	Preferred Term (MedDRA Version 22.1)	Preferred Term Code	Lilly Defined Classification
	Toxoplasmosis (IV)	Cerebral toxoplasmosis	10057854	Narrow
		Eye infection toxoplasmal	10015939	
		Hepatitis toxoplasmal	10019798	
		Meningitis toxoplasmal	10048848	
		Myocarditis toxoplasmal	10028617	
		Pneumonia toxoplasmal	10067566	
		Toxoplasma serology	10050941	Broad
		Toxoplasmosis	10044272	
Non-specific terms	Non-specific terms	None		Narrow
		Delftia acidovorans infection	10081339	
		Sphingomonas paucimobilis bacteraemia	10081563	
		Central nervous system immune reconstitution inflammatory response	10080100	Broad
		Abscess fungal	10000269	
		Alternaria infection	10054207	
		Arthritis fungal	10060966	
		Biliary tract infection fungal	10065203	
		Central nervous system fungal infection	10072805	
		Cerebral fungal infection	10049657	
		Encephalitis fungal	10065170	
		Erythema induratum	10015213	
		Eye infection fungal	10015933	
		Fungaemia	10017523	
		Fungal abscess central nervous system	10017524	
		Fungal endocarditis	10017529	
		Fungal labyrinthitis	10065174	
		Fungal oesophagitis	10049656	
		Fungal peritonitis	10061138	
		Fungal pharyngitis	10076516	
		Fungal retinitis	10068613	
		Fungal sepsis	10058872	
		Fungal urethritis	10081163	
		Hepatic infection fungal	10065217	
		Meningitis fungal	10027236	
		Mycotic endophthalmitis	10063202	

Category	Potential Opportunistic Infection	Preferred Term (MedDRA Version 22.1)	Preferred Term Code	Lilly Defined Classification
		Myocarditis mycotic	10059026	
		Oral fungal infection	10061324	
		Oropharyngitis fungal	10061891	
		Osteomyelitis fungal	10065239	
		Otitis media fungal	10065175	
		Pancreatitis fungal	10065190	
		Pericarditis fungal	10065220	
		Phaehyphomycosis	10034799	
		Pneumonia fungal	10061354	
		Pulmonary mycosis	10037422	
		Pulmonary trichosporonosis	10068184	
		Sinusitis fungal	10058678	
		Splenic infection fungal	10065194	
		Systemic mycosis	10052366	
Pneumonia	Infective Pneumonia SMQ	All PTs	20000231	Narrow

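### The opportunistic-infection rate in SAP 4.6.3.1 is planned only on a wide search list; confirmed cases get no rate, and their classification has no stated blinding

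*SAP*

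**What the plan says.** **Protocol.** Section 8.3.6 lists opportunistic infections, with serious infections, among the AESIs. Section 8.3.6.2 has the sponsor decide which infections are opportunistic, using the published consensus article. Appendix 6 gives examples adapted from that article. It limits several to invasive disease, including "Herpes simplex (invasive disease only"), has no general pneumonia entry, and says it is not exhaustive. Section 9.4.4 allows AESIs to be identified from an SMQ or a sponsor term list.

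**SAP 4.6.3.1, the rate.** "For infections of special interest (serious infections, potential opportunistic infections [POIs], herpes zoster, and herpes simplex), the IR" and its 95% CI will be calculated.

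**SAP 4.6.3.1, the search.** There are two sources. One is a term list: "POIs will be identified from TEAEs based on a Lilly-defined list of MedDRA PTs shown in 6.8". The SAP presents these terms as belonging to the MedDRA system organ class for infections. The other source is the case report form, where the plan is as follows: "a list of all the infection details captured from the infection-specific eCRF (including primary/secondary infecting organism and infection site) will be provided".

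**SAP 4.6.3.1, the classification.** The SAP commits to summarizing each case that meets the case definition, by preferred term within pathogen. It then merges both sources into one list for medical assessment, for "final classification of whether the case definition was met according to the consensus paper after database lock", and ends: "An additional summary may be conducted based on medical assessment".

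**SAP 6.8.** The list ends with the "Infective Pneumonia SMQ", all preferred terms, classed Narrow. Oral, nasal and genital herpes are classed Broad.

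**The concern.** The rate with its confidence interval is the figure a reader will compare between arms. It stops at the search step: it counts events that might be opportunistic, while the protocol's AESI is events that are. In arms of this size, a few ordinary pneumonias could make up most of it.

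The step that separates true cases from search hits is a sponsor judgement, set after database lock. Neither document says whether the assessors know the treatment. The same SAP section plans a listing of treatment-emergent infections that shows the treatment group. What is at stake is whether one protocol-named AESI can be interpreted, and whether the classification behind it can be shown to be independent of treatment.

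**Working it through.** The documents give no opportunistic-infection rate, expected count or precision, so there is no planned figure to reproduce. The check sets the texts side by side, then gives a scale.

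**1. Set counted against AESI.** Protocol 8.3.6.2: infections that meet the consensus definition. SAP rate: infections found by the search. No rate on confirmed cases appears anywhere in SAP 4.6.

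**2. Width of the list.**
- Narrow terms alone already go wider than the protocol's examples, because all Infective Pneumonia SMQ terms are Narrow.
- SAP 6.8 labels terms Narrow or Broad, but SAP 4.6.3.1 does not say which scope feeds the rate. If Broad terms count, oral herpes and bare test names enter as well.
- By hand count, 27 entries name a test or measurement without a result, such as Candida test, Tuberculin test, Interferon gamma release assay and Carbon monoxide diffusing capacity. These are not infections on their face, which sits badly with the description of the list as a subset of the infections SOC. One such code (10070444) is excluded, but only for herpes zoster.

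**3. Herpes simplex.** SAP 4.6.3.1 defines herpes simplex by an entry in 6.8 that it cites as restricted to invasive disease. The entry in 6.8 is headed Herpes simplex (IV), without that restriction. As printed, Genital herpes simplex, Herpes dermatitis and Herpes pharyngitis stand above the row where Broad begins, and Oral herpes and Genital herpes stand below it. Table layout may have shifted in reading, but the headings differ either way. Herpes simplex has its own planned rate, so that rate is affected too.

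**4. Confirmed-case summary.** One sentence commits to summarizing cases that meet the definition. The later one makes the summary based on medical assessment optional. The first depends on a classification that only the later step supplies, so the status of the confirmed-case table is unclear.

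**5. Timing and blinding.** Classification follows lock. The primary lock comes once all participants have completed Week 12 or discontinued treatment (SAP 4.8). Protocol 9.5 and SAP 4.8 protect the blind until an unblinding milestone or decision. Nothing says that the classifiers stay blinded beyond it, or that they finish before it.

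**6. Scale (illustration).** Inputs:
- Arm sizes of 40 and 80, from the sample-size sections; placebo is planned at about 40.
- Assumed full follow-up of 84 or 364 days per participant, ignoring the small loss of time when a participant with an event is censored.
- SAP 4.6 formula: IR = 100 × participants with event / PYO.
- Exact Poisson limits for x events: lower = 100 × χ²(0.025; 2x) / (2 PYO); upper = 100 × χ²(0.975; 2x + 2) / (2 PYO).

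| Arm | Follow-up | PYO | IR from one event (95% CI) |
|---|---|---|---|
| 40 | 12 weeks | 40 × 84 / 365.25 = 9.2 | 10.9 (0.3 to 60.6) |
| 80 | 12 weeks | 80 × 84 / 365.25 = 18.4 | 5.4 (0.1 to 30.3) |
| 40 | 52 weeks | 40 × 364 / 365.25 = 39.9 | 2.5 (0.1 to 14.0) |
| 80 | 52 weeks | 80 × 364 / 365.25 = 79.7 | 1.3 (0.0 to 7.0) |

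Each non-opportunistic event counted as a POI, in a participant with no other counted event, moves the arm's rate by about the amount shown. The 52-week rows overstate time on randomized treatment, because Week 12 nonresponders move to the extension (Protocol 4.1); less time would make the step larger.

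**The case against.** The design is coherent: a sensitive search, organism and site data from the eCRF, then case-by-case review under the same consensus paper as the protocol. Protocol 9.4.4 prespecifies term-list identification, and the SAP labels the rate as potential infections. The SAP does commit to summarizing cases that meet the definition. Protocol Appendix 6 is not exhaustive, so its lack of a general pneumonia entry is not by itself a contradiction. This is a descriptive safety category with no confirmatory role. All of that stands, and it is why the POI rate should be kept.

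Some stronger readings are tempting, but the documents do not support them:

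- *The opportunistic-infection rate is misreported.* It is correctly labelled; it is a rate for a wider set.
- *Oral herpes and test names inflate the rate.* They are Broad terms, and the SAP leaves open whether Broad terms count. A test name would also have to be reported as a TEAE.
- *The classification is unblinded.* After lock does not mean unblinded. The documents refer to a separate Unblinding Plan, and neither says who the assessors are or what they know. The rule in SAP 4.4.3 that withholds results until lock covers PK/PD results only. This is a risk from timing and silence, not a stated procedure.
- *The rate is overstated several-fold.* Any such multiple needs an assumed mix of true and false cases, which the documents do not give.
- *Malignancy review has the same fault.* Its timing is similar ("All cases identified by malignant tumors SMQ will be assessed after database lock by the medical team"), but malignancy is not among the protocol's AESIs, and that review has a different task.

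What the objection leaves untouched: no confirmed-case rate, no stated scope, mismatched herpes simplex headings, an unclear status for the confirmed-case table, and silence on assessor blinding.

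**Conclusion.** The point holds in a limited form. The only rate planned for this AESI is on an unconfirmed set that is wider than the AESI even with Narrow terms alone. The case classification is set after lock without a blinding statement, and the SAP's wording on its output needs reconciling. The herpes simplex rate shares the definition problem.

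The effect is on the interpretation of one descriptive safety category. Neither the size nor the direction of any between-arm effect can be derived. The step of 10.9 (12 weeks) or 2.5 (52 weeks) per 100 patient-years for one event in 40 participants rests on assumed full follow-up and shows sensitivity, not an expected error. The change is worth making because it improves a stated timing and a stated analysis set, using a review that is already planned.

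**What to change.** In SAP 4.6.3.1 and 6.8:

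1. Have the existing medical reviewers classify all cases against the consensus definition, blinded to treatment, and complete this before unblinding at each lock. Give them case material without the treatment column.
2. Make the by-arm table and the incidence rate with 95% CI on confirmed opportunistic infections a stated analysis, replacing the present mix of firm and optional wording.
3. Keep the POI rate beside it, labelled as a sensitive screen, and state whether it uses Narrow terms or Narrow plus Broad.
4. State whether bare test names count, and correct the description of the list as a subset of the infections SOC if they remain.
5. Reconcile the herpes simplex entry in 6.8 with the invasive-disease wording in SAP 4.6.3.1 and Protocol Appendix 6.

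The cost is SAP wording plus a few days of review before unblinding. Cases that arise after the primary lock would need assessors who are kept blinded. No clinical procedure changes.

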Tuberculosis (TB) test	X									Patients who had a tuberculin skin test (TST) will return from 48 to 72 hours after placement to have the test result read. Samples may be sent to central or local laboratory based on the type of test. A local laboratory must be qualified by local regulations.
Human immunodeficiency virus (HIV) screening tests	X									
Hepatitis C virus (HCV) screening tests	X									HCV RNA will be measured to confirm positive hepatitis C virus antibody.
Hepatitis B virus (HBV) screening tests	X									Includes testing for HBsAg and anti-HBc.

Table 1. Schedule of Activities for the Screening and Induction Treatment Periods of Study J1P-MC-KFAH										
V1 and V9 procedures may be conducted over more than 1 day as long as all activities are completed within the allowable visit tolerance and all scheduled activities are completed prior to dosing.										
For procedures at an ETV, see ETV in Table 4.										
For procedures at an unscheduled visit, see V997 in Table 4.										
Visit number	V1	V2	V3	V4	V5	V6	V7	V8	V9	Comment
Weeks from randomization	-5	—	1	2	4	6	8	10	12	
Study day	—	1	8	15	29	43	57	71	85	
Visit interval tolerance (days)	≤35 before V2	—	±3	±3	±3	±3	±3	±3	±3	
Fasting visit		X							X	
HBV DNA	X								X	Only for participants who are positive for anti-HBc at screening.
Pharmacokinetic (PK) samples		X	X	X	X		X		X	Collect samples before dosing, if dosing is scheduled. Collect additional samples at specified times relative to onset of hypersensitivity events.
CCI		X		X	X		X		X	Collect samples before dosing, if dosing is scheduled. Collect additional samples at specified times relative to onset of hypersensitivity events.
Flow cytometry panel		X		X					X	
Genetics sample		X								Blood sample for DNA pharmacogenetics can be obtained any time at or after V2.
CCI		X			X		X		X	
Endoscopic Procedure										
Endoscopy	X								X	Screening endoscopy must occur ≤14 days prior to randomization. At screening, perform only for participants who are eligible for the study by all other study entry criteria.
Colon biopsy sample collection	X								X	Performed at time of endoscopy. Instructions for collection are provided in the lab manual. Flexible sigmoidoscopy is recommended, except for protocol-specified reasons when a colonoscopy should be performed.

Table 1. Schedule of Activities for the Screening and Induction Treatment Periods of Study J1P-MC-KFAH										

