- 19h. Any investigational nonbiologic therapy within 4 weeks prior to the screening endoscopy or within 5 half-lives prior to the screening endoscopy, whichever is longer.
- 19i. Any investigational biologic therapy, not otherwise mentioned, within 8 weeks prior to the screening endoscopy or within 5 half-lives prior to the screening endoscopy, whichever is longer.
- 19j. Leukocyte apheresis (leukapheresis, for example, Adacolumn®) within 3 weeks prior to screening endoscopy.
- 19k. Interferon therapy within 8 weeks prior to screening endoscopy.
- 20. Have failed 3 or more classes of advanced therapies approved for treatment of UC.

Infections and Infectious Disease

- 21. Have or have had active tuberculosis (TB) or latent tuberculosis infection (LTBI):
 - 21a. Have current active TB or past history of active TB (see Section 8.2.6).
 - 21b. Have LTBI, or have had LTBI that has not been treated with a complete course of appropriate therapy as defined by the WHO and/or the United States Centers for Disease Control and Prevention (see Section 8.2.6).

Note: Patients who have a documented history of completing an appropriate TB prophylaxis regimen with no history of risk of re-exposure since completing their treatments and with no evidence of active TB may be eligible to participate in the study, provided all other study eligibility criteria are met.

- 22. Have HIV infection, or AIDS, or test positive for HIV antibodies at screening.
- 23. Have a current infection with hepatitis B virus (that is, positive for hepatitis B surface antigen [HBsAg] and/or PCR positive for HBV DNA) (Section 8.2.7).
- 24. Have a current infection with hepatitis C virus (that is, positive for HCV RNA) (Section 8.2.8).
- 25. Have *C. difficile* or other intestinal infection within 30 days of screening endoscopy, or test positive at screening for *C. difficile* toxin or for other intestinal pathogens.
- 26. Have a confirmed diagnosis of cytomegalovirus-associated colitis.

Note: Patients may be eligible if they have had adequate treatment of this condition and have resolution of symptoms at least 3 months prior to screening endoscopy, provided all other study eligibility criteria are met.

27. Have serious, opportunistic, or chronic or recurring extraintestinal infections that are not adequately treated or that require antibiotics during the period from 30 days prior to screening until baseline (Visit 2). Such infections include, but are not limited to, the following:

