8.2.7. Hepatitis B Testing and Monitoring

Initial testing for HBV infection includes hepatitis B surface antigen (HBsAg) and antibody to hepatitis B core antigen (anti-HBc).

- If HBsAg is positive, the participant is excluded.
- If HBsAg is negative and anti-HBc is negative, the participant is not excluded.
- If HBsAg is negative and anti-HBc is positive, further testing for HBV DNA is required.
 - If the screening HBV DNA is positive, the participant is excluded.
 - If the screening HBV DNA is negative, the participant is not excluded. Repeat testing for HBV DNA is required at least approximately every 8 to 14 weeks during the study (see the timing in the SoA), with temporary withholding or permanent discontinuation of study intervention if HBV DNA is positive, as described in Section 7.

Management of enrolled participants with detectable HBV DNA during the study

If HBV DNA is detected during the study, the study drug will be temporarily withheld or discontinued and participants should receive appropriate follow-up medical care as described in Section 7.

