Pregnancy test – serum	Assayed by Lilly-designated laboratory. To be performed only on women of childbearing potential and women with history of tubal ligation.
Pregnancy test – urine	Evaluated locally. To be performed only on women of childbearing potential and women with history of tubal ligation. Result must be negative before dosing at each dosing visit.
Follicle-stimulating hormone (FSH)	Assayed by Lilly-designated laboratory Optional, performed to confirm postmenopausal status.

	Notes
Additional Testing	Assayed by Lilly-designated laboratory. Results will not be provided to the investigative sites.
CCI	

	Notes
TB, HIV, and Hepatitis Serology	
Tuberculosis (TB) test:	TB test based on local standard of care
QuantiFERON®-TB Gold test	Assayed by Lilly-designated laboratory.
T-SPOT®. TB	Evaluated locally. Local laboratory must be qualified by local regulations.
Tuberculin skin test (TST)	Local testing. Local laboratory must be qualified by local regulations.
Human immunodeficiency virus (HIV)	Assayed by Lilly-designated laboratory.
Hepatitis C virus (HCV) testing:	Assayed by Lilly-designated laboratory.
Hepatitis C antibody	
HCV RNA	
Hepatitis B virus (HBV) testing:	Assayed by Lilly-designated laboratory.
Hepatitis B surface antigen (HBsAg)	
Hepatitis B core antibody (anti-HBc)	
HBV DNA	Performed only for participants who test positive for anti-HBc.

	Notes
Pharmacokinetics (PK) Samples	Assayed by Lilly-designated laboratory. Results will not be provided to the investigative sites.
LY3471851 concentration	

	Notes
	Assayed by Lilly-designated laboratory. Results will not be provided to the investigative sites.

	Notes
Flow Cytometry	Assayed by Lilly-designated laboratory. Results will not be provided to the investigative sites.
Lymphocyte subsets - T regulatory cells	
T-cell subsets	

	Notes
Genetics Samples	Assayed by Lilly-designated laboratory. Results will not be provided to the investigative sites.
Genetics sample	

	Notes
	Assayed by Lilly-designated laboratory. Results will not be provided to the investigative sites.
	Endoscopic biopsy sample collection

	Notes
Stool Samples	Assayed by Lilly-designated laboratory.
Stool culture	
Clostridium difficile testing	Confirmed by a test for C. difficile toxin gene expression.
CCI	Results will not be provided to the investigative sites.

Clinical Laboratory Calculations

eGFR (MDRD)

- For creatinine results reported in conventional units (mg/dL):

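### The SAP splits its HBV DNA summary by baseline surface-antibody status, which the protocol does not measure, and by core-antibody-negative strata, which have no scheduled HBV DNA tests

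*SAP*

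**What the plan says.** SAP 4.6.3.1, under HBV DNA, plans two outputs. The first is a listing of patients with detectable HBV DNA. The second is a table in which HBV DNA status, in three levels cut at 29 IU/mL (not detectable, detectable but not quantifiable, quantifiable), "will be summarized by treatment group stratified by baseline HBV serology status, specifically": HBsAb-/HBcAb-, HBsAb+/HBcAb-, HBsAb+/HBcAb+ and HBsAb-/HBcAb+.

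The protocol describes hepatitis B screening in three places.

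- Schedule of Activities, Table 1, on the HBV screening tests: "Includes testing for HBsAg and anti-HBc".
- Section 8.2.7: "Initial testing for HBV infection includes hepatitis B surface antigen (HBsAg) and antibody to hepatitis B core antigen (anti-HBc").
- Appendix 2 (10.2.1): the hepatitis B entries are HBsAg, anti-HBc and HBV DNA, the last with the note "Performed only for participants who test positive for anti-HBc".

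For HBV DNA, Table 1 carries the comment "Only for participants who are positive for anti-HBc at screening", and the same restriction is attached to the HBV DNA rows of Tables 2, 3 and 4. Exclusion criterion 23 removes patients who are "positive for hepatitis B surface antigen [HBsAg] and/or PCR positive for HBV DNA".

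**The concern.** A stratified table needs the stratifying variable at baseline and the outcome within each stratum. Here the SAP asks for surface antibody, while the protocol measures surface antigen. It also asks for HBV DNA results in core-negative participants, for whom no such test is scheduled.

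The protocol takes reactivation seriously. Section 8.2.7 calls for repeat HBV DNA testing about every 8 to 14 weeks in anti-HBc-positive participants, Visit 802 exists only for them, and Section 7 ties withholding or discontinuation of study drug to the result. SAP 4.6.3.1 promises a summary of this monitoring. If its strata do not match the data collected, the programmer must redefine the table after the data are in, when the definition should already be settled.

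**Working it through.** No arithmetic model applies. The check sets each SAP stratum against what the protocol collects.

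**Is there a baseline surface-antibody result?** Table 1, Section 8.2.7 and Appendix 2 all name HBsAg and anti-HBc, and none names anti-HBs. The protocol lists anti-HBs as a test only in Appendix 5, the hepatic evaluation panel. That panel is used under Section 8.2.9 after liver-test elevations during the study. A result obtained that way is post-baseline and exists only for participants with such an event, so it cannot define baseline serology.

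**Who has HBV DNA results?** Section 8.2.7 states "If HBsAg is negative and anti-HBc is positive, further testing for HBV DNA is required". For the other enrolled group it states only "If HBsAg is negative and anti-HBc is negative, the participant is not excluded", with no DNA test attached. The scheduled times, all with the same anti-HBc restriction, are:

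- screening and Visit 9;
- Visits 15, 21 and 27 for Week 12 Responders;
- Visits 16, 22 and 27 for Week 12 Nonresponders;
- the early termination visit (ETV) and Visit 802.

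**Strata against data:**

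| SAP stratum | Baseline HBsAb measured? | Scheduled HBV DNA? | If HBsAb means HBsAg |
|---|---|---|---|
| HBsAb- / HBcAb- | No | No | Enrolled, no scheduled HBV DNA |
| HBsAb+ / HBcAb- | No | No | Excluded (criterion 23) |
| HBsAb+ / HBcAb+ | No | Yes | Excluded (criterion 23) |
| HBsAb- / HBcAb+ | No | Yes | Enrolled, HBV DNA scheduled |

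**Literal reading.** None of the 4 strata can be formed as defined. The two core-negative strata also have no scheduled outcome. The two core-positive strata have the outcome but cannot be told apart, so they collapse into one group.

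**Slip reading (HBsAg intended).** All 4 strata can be formed. Two are empty through exclusion and one has no scheduled tests, which leaves 4 - 2 - 1 = 1 informative stratum.

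Both readings end at the same group: anti-HBc positive and HBsAg negative. Because a positive screening HBV DNA result also excludes, everyone in that group should enter with negative HBV DNA. The post-baseline results are therefore what the table can usefully show.

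**The case against.** The strongest reply is that this is a labelling error in a minor table. HBsAb may simply be a slip for HBsAg. In that case every stratum can be formed, the row that matters is correctly defined, and the empty rows do no harm. Even on the literal reading, core-antibody status is known, and a sensible programmer would collapse the rows or show surface antibody as missing. SAP 4.1 allows a change that does not touch a principal feature of the protocol to be described in the study report. Much of this stands: the defect is in the stratum definitions, and the core-positive data can be tabulated. It does not make the table correct as written, since on either reading three of the four rows are uninformative or cannot be separated.

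A reader might go further and draw two inferences that the documents do not support.

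- *That untested participants would be counted as not detectable, diluting the detection rate.* SAP 4.1.1 computes percentages over non-missing observations. The table also keeps treatment groups and serology strata apart, so untested core-negative participants would not enter a core-positive denominator.
- *That hepatitis B reactivation would go unreported at group level.* The listing of detectable HBV DNA applies whatever the serology. SAP Appendix 8 has an HBV reactivation category within the potential opportunistic infections, for which 4.6.3.1 plans a summary and an incidence rate with a 95% CI.

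It is also too strong to say that core-negative participants can have no HBV DNA result at all. Appendix 5 allows reflex HBV DNA in a hepatic work-up. Such results would be sporadic and would still lack a baseline surface antibody.

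**Conclusion.** The point holds for the stratification. The HBsAb split cannot be derived from baseline data, and the two HBcAb-negative strata have no scheduled HBV DNA results. Reading HBsAb as HBsAg makes the categories derivable but still leaves only the anti-HBc-positive group informative.

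The reach is limited. This is one descriptive safety table with no planned hypothesis test and no bearing on the primary analysis. It is, however, the only group-level summary of HBV DNA laboratory monitoring. The opportunistic-infection output rests on reported adverse-event terms and infection case-report-form details, and does not replace it.

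The conclusion assumes that the protocol from which the SAP was written has the same hepatitis B panel as the one supplied. The SAP cites a protocol dated 18Nov2020, and the visible part of the supplied protocol's list of changes mentions no hepatitis B test.

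**What to change.** In SAP 4.6.3.1, replace the four strata with one population: anti-HBc-positive, HBsAg-negative participants with at least one post-baseline HBV DNA result. Within it, summarise the three existing status levels:

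- by assigned treatment group, in line with the Safety Population in SAP Section 3, which is analysed as assigned;
- by study period and visit, including the ETV and Visit 802. The period split matters because Week 12 Nonresponders assigned to placebo receive LY3471851 from Week 14;
- with participants tested at that time as the denominator, as SAP 4.1.1 already implies.

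Keep the listing of detectable HBV DNA unchanged, so that any event-driven result outside this population still appears.

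The cost is a wording change in one SAP subsection and its table shell. It needs no new assay, sample or protocol change.
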